#### **11c. Measurement tools used**

Pulmonary function test (FEV1)

Quality of life questionnaire (*see attached*)

Rev\_2/5/16 Page 6 of 10

**Research Protocol**  
**Lung Institute Dallas**

#### **11e. Safety considerations/Patient safety**

The safety of research participants is foremost. Strict policies and procedures and standard operating procedures have been developed to ensure the safety of patients during the stem cell retrieving and administration procedures. Adverse events, as well as near-miss events are reported to the Principal Investigator, Medical Director, Compliance Department, and the Quality Improvement & Risk Management (QI&RM) Committee. The Lung Institute's management services company, Regenerative Medicine Solutions (RMS) provides continuous oversight and closely monitors the adherence to regulatory standards and policies and procedures. The Compliance Program ensures that all staff are trained on the appropriate identification and reporting of adverse events and near-misses, including potential breaches in protocols or patient safety and privacy standards.

Patient safety and risk management protocols are incorporated throughout our Policies & Procedures (P&Ps) and the oversight and trending of our protocols, as well as their effectiveness and adherence is monitored by and reported to the Quality Improvement & Risk Management (QI&RM) Committee.

Patient's protected health information is also strictly protected; adherence to HIPAA & HITECH standards are continuously monitored by the Compliance Department. Staff is trained on protection of patient health information protocols within the first 30 days from hire, and annually thereafter.

All Lung Institute Dallas clinical staff are trained in the protection of human subjects for research. Additionally, each clinical staff member is trained on job functions and assessed for competency on an annual basis.

### **11f. Data monitoring and Storage**

The Compliance department of Regenerative Medicine Solutions will oversee the conduct of research and data management.

Although identifying information will not be used for the final presentation of findings, data *will not* be de-identified at the point of collection or storage. Texas Medical Board code requires that full contact information be kept on all stem-cell treated patients and available for presentation to the Board within 14 days if requested.

## **12. STATISTICAL CONSIDERATIONS AND DATA ANALYSIS**

### **12a. Sample size**

The anticipated sample size for this study is two hundred patients.

### **12b. Statistical methods**

For the quantitative, descriptive arm of this study, sample characteristics will be collected to include age, sex and diagnosis. Pre- and post-treatment FEV1 measurements will be collected on each patient and evaluated by simple measures of central tendency (mean, median and mode). Sufficient descriptive data will be collected and reported to encourage replication of our study.

For the qualitative, anecdotal arm of the study, Lung Institute utilizes CCQ, the Clinical COPD Questionnaire to document patient's perceptions on improved quality of life. The information will be collected and interpreted by evaluating for common themes within the anecdotes. As a note regarding the rigor of qualitative research: is important in qualitative research to ensure that the study is credible and trustworthy (Smith, Flowers and Larkin, 2009). A number of guidelines for assessing this quality look toward establishing credibility. Psychologist Lucy Yardley's work in 2000 provides the principles for assessing the quality of qualitative research and how the interpretive phenomenological method can address them. First, the study must provide good *sensitivity to context*. In this study, the immersion in the clinic through field experience, the existing literature on COPD and stem cell treatment, and the anecdotes obtained

Rev\_2/5/16 Page 7 of 10

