## **5. HYPOTHESES**

### **5a. Primary Hypothesis/Quantitative Arm**

Null hypothesis: Following autologous stem cell treatment for chronic lung disease, patients will have no improvement in pulmonary function (measured by FEV1) at six months

Alternative hypothesis: Following autologous stem cell treatment for chronic lung disease, patients will have an increase in pulmonary function (measured by FEV1) of 5 to 10% or more

Rev\_2/5/16 Page 2 of 10

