## 6. STUDY DESIGN

This study uses a concurrent mixed-methods approach to collect and analyze both qualitative and quantitative data. The *quantitative* arm will use a non-experimental, descriptive approach to measure and analyze pre- and post-stem cell treatment pulmonary function test results of treated patients. Measurement of the occurrence of adverse events will also be part of the quantitative arm.

Pre-treatment pulmonary function test results (measured by FEV1) will be compared with a six-month post-treatment pulmonary function test result (FEV1) for each patient. The aim of this method is to generalize an improvement in pulmonary function (measured by FEV1) among the general population of all individuals treated by autologous cell therapy for chronic lung disease.

The *qualitative* arm of the study uses an interpretive phenomenological approach to collect and analyze pre- and post- cell therapy anecdotal data regarding perceived quality of life among treated patients. Phenomenological research involves investigating the lived experience.

Qualitative research has several assumptions (D. Nicholls, 2009; Ritchie & Lewis, 2003). Primarily, there is no predetermined theoretical framework- rather the theory, if any, is derived from the data. Secondly, qualitative research is context-driven. Finally, qualitative researchers focus on the *emic* perspective that concerns itself with the view, perspectives and descriptions of others.

This study uses an *interpretive phenomenological analysis* (IPA) approach throughout the study from planning to data collection to analysis. This methodology is used to illuminate each participant's variation of the same general phenomenon (in this case, COPD) (Reissman, 2008; Ritchie & Lewis, 2003).

Data from both arms of the study will be combined following data collection for analysis, discussion and presentation. Safety data on adverse outcomes will be tracked and reported separately as a descriptive, quantitative analysis.

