#### **11b. Randomization**

Neither the participants, nor the investigator, or those assessing/analyzing the outcome(s), will be blind (or masked) to group assignment; all patients will receive treatment.

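### Section 5a sets a null and a 5 to 10% FEV1 target, but section 12b summarises FEV1 only by averages, with no defined change, no precision and no decision rule

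*Combined protocol and SAP*

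**What the plan says.** Section 5a gives a formal pair for the primary hypothesis. Under the null, "patients will have no improvement in pulmonary function (measured by FEV1) at six months". Under the alternative, "patients will have an increase in pulmonary function (measured by FEV1) of 5 to 10% or more".

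Section 6 says how these are to be addressed: "Pre-treatment pulmonary function test results (measured by FEV1) will be compared with a six-month post-treatment pulmonary function test result (FEV1) for each patient". It then states an inferential purpose: "The aim of this method is to generalize an improvement in pulmonary function (measured by FEV1) among the general population". The same section calls this arm a "non-experimental, descriptive approach to measure and analyze" exercise, and section 12b repeats the descriptive label.

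Section 12b contains the only FEV1 analysis: "Pre- and post-treatment FEV1 measurements will be collected on each patient and evaluated by simple measures of central tendency (mean, median and mode". A general promise follows to report enough descriptive data for others to replicate the study. No spread, interval, test or success criterion is named there or elsewhere.

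Section 12a reads "The anticipated sample size for this study is two hundred patients", with nothing attached to the figure. Section 11b confirms a single group: "all patients will receive treatment".

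The pulmonary function test (PFT) is listed among the vitals in the Venous Procedure SOP (step 11) and the Bone Marrow Aspirate SOP (step 9). Both steps apply on first and later treatment days, and the test may be done within three days of scheduled treatment. No test is designated as the study baseline.

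**The concern.** The plan asks an inferential question and supplies a tool that cannot answer it. Two sets of averages show whether the later one is higher. They do not show whether the difference exceeds what chance would produce, or whether it meets the 5 to 10% target. With no rule fixed in advance, any positive difference could be reported as improvement.

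The target itself can be read in several ways. Section 5a does not say what the percentage is a percentage of, whether it applies to the mean or to each patient, or whether 5% or 10% decides. If these choices and the baseline test are made after the data are seen, the most favourable combination can be selected. This matters because section 3 intends the results for the public and the medical community, and section 13 lists the same FEV1 gain as a potential benefit of treatment.

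**Working it through.** **1. What is needed against what is supplied.**

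| Needed for 5a and 6 | Supplied |
|---|---|
| A change variable for each patient | Comparison announced in 6; variable not defined in 6 or 12b |
| Spread and precision of the mean change | None |
| Rule for rejecting the null | None |
| Unit, level and threshold of the target | A range only |
| One named baseline test | PFT on repeated treatment days; none designated |

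**2. The plan's own figure.** The 200 in section 12a cannot be reproduced, because no alpha, power, SD or dropout is given. Inverting n = (SD × (z_alpha + z_power)/delta)² for a 5-point change at two-sided 0.05 gives SD = 5 × √200/(1.960 + 0.842) = 25.2 for 80% power, and 5 × √200/(1.960 + 1.282) = 21.8 for 90%. These are back-calculations and not statements of the plan.

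**3. Illustration.** Assumptions, none of them in the documents: SD of the within-patient relative change 10 to 20 percentage points, with 30 as a stress case; normality; and 100 pairs as an example of incomplete follow-up.

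- Half-width of the 95% CI: t(0.975, n−1) × SD/√n. Example: 1.972 × 20/√200 = 2.79.
- Chance of a group mean gain of 5 or more with zero true change: 1 − Φ(5/(SD/√n)). Example: 1 − Φ(5/1.414) = 1 − Φ(3.54) = 0.0002.
- Share of patients gaining 5% or more with zero mean change: 1 − Φ(5/SD). Example: 1 − Φ(0.25) = 0.401.

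| SD | Half-width, n=200 | Half-width, n=100 | P(mean ≥ 5), n=200 | P(mean ≥ 5), n=100 | Patients ≥ 5% |
|---|---|---|---|---|---|
| 10 | 1.39 | 1.98 | <0.01% | <0.01% | 30.9% |
| 15 | 2.09 | 2.98 | <0.01% | 0.04% | 36.9% |
| 20 | 2.79 | 3.97 | 0.02% | 0.6% | 40.1% |
| 30 | 4.18 | 5.95 | 0.9% | 4.8% | 43.4% |

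With zero true change the mean change is positive with probability 0.5 at any SD and n.

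**4. Why the paired change is needed.** With complete pairs, the difference of the two means equals the mean change, but its precision cannot be recovered from separate summaries. With equal variances and correlation r, treating the two sets as independent inflates the standard error by 1/√(1 − r): 2.24-fold at r = 0.80 and 4.47-fold at r = 0.95 (r assumed). If some six-month tests are missing, the two averages also describe different patients.

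**The case against.** The strongest defence is the descriptive label in sections 6 and 12b. It has force: a descriptive arm does not need a formal test, and the lack of one would not by itself be a defect. But the label sits beside a null and alternative and an aim to generalise, and a descriptive before-after study still has to report the change and its spread.

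Four stronger readings are tempting and are not supported.

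- A reader might infer that no within-patient comparison is planned. Section 6 plans one for each patient; what is missing is its definition and analysis.
- A reader might infer that chance alone would readily produce the stated target. For the group mean it would not: at 200 pairs the probability of reaching 5 points is below 1% even at SD 30. The exposure lies in calling a smaller positive difference an improvement, or in counting individual patients.
- A reader might infer that the discharge-day PFTs (Discharge SOP, steps 7 and 15) could serve as baseline. They come after treatment has begun, and step 15 follows the marrow procedure, so the plain meaning of pre-treatment sets them aside. The three-day wording may also mean one test per treatment episode. The point that stands is narrower: no test is designated.
- A reader might infer that the six-month test is merely optional. Procedure CL-005, section H, only advises it, but section 11 of the protocol says it will be done. The two passages need reconciling.

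Two further objections are fair. A null of zero paired with a target effect is common, so the gap between 0 and 5% is not itself an error. And the documents never mention percent predicted; relative change is the natural reading of the target, although the unit is still not stated.

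**Conclusion.** The point holds. Followed exactly, the plan cannot separate a mean FEV1 change from chance or decide its own primary hypothesis, and its target is not specific enough to be met or missed. That conclusion comes from the text alone. The sizes rest on assumed SDs: the unreported uncertainty is about ±1.4 to 2.8 points at 200 pairs (±4.2 at SD 30), which is not small beside a 5% target. The choice of level matters more. Read per patient, 31 to 40% (43% at SD 30) would meet 5% with no mean change at all, assuming normality, whereas the group mean would almost never do so. The matter should be settled before six-month FEV1 data are summarised.

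**What to change.** **Section 12b.** Make the primary FEV1 summary each patient's change from one named pre-treatment PFT (the last one before the first treatment) to the six-month test. Report the number of patients with both tests, the mean change, SD and two-sided 95% CI (paired t).

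**Section 5a.** State the unit, that the target applies to the group mean, and one threshold from the stated range. Conclude improvement only if the lower confidence limit exceeds 0, and report where the interval lies relative to the threshold. For a true 5-point change with 200 pairs, this rule has about 94% power at SD 20 and 65% at SD 30 (normal approximation, SDs assumed).

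**Alternative.** If the arm is to stay purely descriptive, drop the null and alternative from 5a and the generalising aim from section 6, and report the same paired change with its interval.

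**Either way**, describe the result as an uncontrolled before-after change.

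**Cost.** Wording in 5a, 6 and 12b and a little more analysis, using values already collected. The headline may be less favourable. Patients without a PFT before first treatment or at six months would not contribute. The interval deals with chance only; it does not repair missing six-month tests or the lack of a control group.

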## **4. RESEARCH QUESTIONS**

The research questions to be informed by this investigation are as follows:

1. Is the collection and administration of autologous stem cells for the treatment of chronic lung disease safe?
2. Does treatment with autologous stem cells for chronic lung disease improve measurements of pulmonary function (specifically FEV1)?
3. Does treatment with autologous stem cells for chronic lung disease improve the patient's perceived quality of life?

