## 8. STUDY POPULATION

Lung Institute Dallas  
[name]  
[name]

Populations that may participate vary by selected treatment of those offered by the Lung Institute. Candidates are eligible for treatment if they are diagnosed with Chronic Obstructive Pulmonary Disease and are not excluded by one or more of several disqualifiers that vary by treatment type offered by the Lung institute.

Rev\_2/5/16 Page 3 of 10

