### 9a. Inclusion criteria

The community eligible for treatment with the Lung Institute are those diagnosed with COPD and ILD. Populations diagnosed with COPD were estimated by the American Lung Association in 2012 to be:

- US: 15,340,484
- Texas : 984,708
- Dallas County : 87,305
- Denton County : 24,614
- Collin County: 30,285

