## 10. STUDY OUTCOMES

The anticipated outcomes of this study are a minimization of adverse events, an improvement in pulmonary function testing (measured by FEV1), and an improvement in self-reported quality of life indicators.

Rev\_2/5/16 Page 5 of 10

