**PROCEDURES:**

**A. PROCEDURE INCLUSION CRITERIA**

**1. FOR ALL PROCEDURES**

- a) DIAGNOSIS OF COPD; OR
  
- b) DIAGNOSIS OF ILD AND/OR A DIAGNOSIS THAT FALLS UNDER THE VARIOUS ILD DISORDER/DISEASES; AND ILD DISORDERS/DISEASES INCLUDE, BUT ARE NOT LIMITED TO:
  - i. INTERSTITIAL PNEUMONIA
  - ii. IDIOPATHIC PULMONARY FIBROSIS AND/OR OTHER PULMONARY FIBROSIS
  - iii. SARCOIDOSIS
  - iv. NONSPECIFIC INTERSTITIAL PNEUMONITIS: INTERSTITIAL LUNG DISEASE THAT'S OFTEN PRESENT WITH AUTOIMMUNE CONDITIONS (SUCH AS RHEUMATOID ARTHRITIS OR SCLERODERMA).
  - v. HYPERSENSITIVITY PNEUMONITIS
  - vi. ASBESTOSIS
- c) MEET AGE REQUIREMENT (16 YEARS OR OLDER); AND
- d) CHEST X-RAY OR CT SCAN OF LUNGS SHOWING FIBROSIS AND/OR CHRONIC INFLAMMATION
  - i. DOCUMENTATION OF DIAGNOSIS MAY BE CAPTURED IN OTHER NOTES IF SCAN X-RAY OR SCAN IS NOT AS DESCRIPTIVE.

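### If ILD patients are in the study, its outcome sections give them only FEV1 and a COPD questionnaire, so the efficacy answer for ILD is weak and hard to interpret

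*Combined protocol and SAP*

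**What the plan says.** **Who is studied.** Section 8 (Study Population) reads "Candidates are eligible for treatment if they are diagnosed with Chronic Obstructive Pulmonary Disease". Section 9a reads "The community eligible for treatment with the Lung Institute are those diagnosed with COPD and ILD". Policy CL-005, part A, accepts as an alternative to COPD a "DIAGNOSIS OF ILD AND/OR A DIAGNOSIS THAT FALLS UNDER THE VARIOUS ILD DISORDER/DISEASES", and lists among the examples "IDIOPATHIC PULMONARY FIBROSIS AND/OR OTHER PULMONARY FIBROSIS", sarcoidosis and asbestosis. The Introduction and the CL-005 policy statement also name both diseases.

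**What is asked.** Research question 2 (section 4) is whether treatment for chronic lung disease will "improve measurements of pulmonary function (specifically FEV1". Question 3 asks the same of perceived quality of life. The alternative hypothesis in section 5a is that "patients will have an increase in pulmonary function (measured by FEV1) of 5 to 10% or more". Section 6 aims to generalise the FEV1 result to everyone given this therapy for chronic lung disease.

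**What is measured and analysed.** The efficacy outcomes in section 10 are "an improvement in pulmonary function testing (measured by FEV1), and an improvement in self-reported quality of life indicators". Section 11c lists FEV1 and a quality-of-life questionnaire. Section 12b summarises FEV1 by mean, median and mode, and says of quality of life that "Lung Institute utilizes CCQ, the Clinical COPD Questionnaire to document patient's perceptions on improved quality of life", with the material then read for themes. Diagnosis is collected as a sample characteristic, with no analysis by diagnosis. FVC is mentioned nowhere.

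**The concern.** The efficacy questions are put for COPD and ILD together, but one named instrument is a COPD questionnaire by its own title and the other is FEV1 alone. In fibrotic lung disease the main spirometric change is loss of volume, which FVC measures directly and FEV1 follows only indirectly. That premise is general knowledge of spirometry; the documents do not state it.

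This is a matter of fit between measure and disease, not only of case mix. Splitting the FEV1 and CCQ results by diagnosis would still leave ILD patients with the same two measures. At stake is a published statement about lung function and quality of life in chronic lung disease that a reader would take to cover ILD, without a measure suited to ILD behind it.

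**Working it through.** The plan has no figure to reproduce here: 200 patients (section 12a) is given without a standard deviation, error rates or a COPD/ILD split. The check is mainly one of text against text.

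**1. Is ILD in the study?**
- COPD only: section 8. The population counts in sections 8 and 9a are also for COPD alone, and section 6 names COPD as the phenomenon studied in the qualitative arm.
- COPD and ILD: Introduction, section 9a, CL-005 policy statement, CL-005 part A.

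The texts conflict, and nothing in them says which prevails.

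**2. If ILD is in, which efficacy measures apply to it?** Sections 10, 11c and 12b give FEV1 and the questionnaire. None names a measure or a separate analysis for ILD.

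**3. Do other variables fill the gap?** The Introduction lists the six minute walk, oxygen use, infections and other hoped-for changes. CL-005 part H advises a walk test and pulse oximetry at 6 months. The outcome and analysis sections carry none of these forward. Oxygen saturation is taken before treatment (Venous SOP step 11, Bone Marrow SOP step 9), but neither SOP schedules a walk test, so no before/after comparison of walking distance is possible as planned.

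**4. Is FVC within reach?** A lung function test is listed before treatment in those same SOP steps and at 6 months in section 11 and CL-005 part H. On the general-knowledge premise that a spirometry giving FEV1 also gives FVC, no new test or visit is needed.

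**5. How many patients?** Assumed ILD share 10 to 40%: 200 × 0.10 = 20; 200 × 0.40 = 80. If section 8 governs, 200 × 0 = 0.

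**6. What would a pooled FEV1 mean show?** Suppose, for illustration, a gain of 5 points in COPD and 0 in ILD. Pooled mean = 5 × (1 − ILD share).
- 10%: 5 × 0.90 = 4.5
- 20%: 5 × 0.80 = 4.0
- 40%: 5 × 0.60 = 3.0

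The pooled figure describes neither disease and conceals the ILD result.

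**7. What does separation cost in precision?** The plan specifies no interval; this only sizes the trade-off. 95% half-width = 1.96 × SD / √n, with an assumed SD of FEV1 change of 15 points, so 29.4 / √n, and every patient measured at 6 months.
- All 200 pooled: 29.4 / √200 = 2.1
- 10% share: COPD, n = 180, 29.4 / √180 = 2.2; ILD, n = 20, 29.4 / √20 = 6.6
- 40% share: COPD, n = 120, 29.4 / √120 = 2.7; ILD, n = 80, 29.4 / √80 = 3.3

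At n = 20, an SD of 10 or 20 gives 4.4 or 8.8. The COPD estimate loses little; the ILD estimate may be imprecise, which a pooled figure would hide.

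**The case against.** The best reply is that ILD may not be in the study at all. If section 8 is the operative text, the mismatch disappears. This stands, and it is why reconciliation comes first. Even then the wording of the questions and of the generalisation would need narrowing to COPD.

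Second, quality of life is more than a CCQ result. Section 11 adds journals, section 6 an interpretive analysis of patients' accounts, and section 5c several indicators; an ILD patient can contribute to all of them. No analysis of CCQ scores is specified, and the attached questionnaire is not in the text available, so its unsuitability for ILD is inferred from its name. This stands as a limit: the point concerns a COPD-based assessment in a COPD-framed arm, not a biased score.

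Third, other lung function values may already reach the medical record, since the SOPs require testing to be documented there. True, but none is named for analysis.

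Fourth, an uncontrolled, descriptive study will not establish efficacy in ILD merely by adding FVC. Also true. The change gives ILD a relevant description; it does not supply a comparison.

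A reader might go further and infer that the study cannot answer its efficacy questions for ILD, that FEV1 and the CCQ are the only efficacy variables anywhere in the documents, or that FEV1 was picked for COPD. The documents support none of these. Question 2 is defined as FEV1, which can be measured and tabulated in ILD; other variables are named outside the outcome sections; and no reason for choosing FEV1 is given.

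**Conclusion.** The point holds conditionally. The eligibility texts contradict one another and must be reconciled. If ILD is in, sections 10, 11c and 12b contain no measure suited to it and no separate reporting, while the questions and intended generalisation include it. The efficacy answer for ILD would be weak and hard to interpret, though not absent.

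The number of patients affected is unknown: 20 to 80 of 200 under an assumed share of 10 to 40%, and none if section 8 governs. The conclusion also rests on the premise, from outside the documents, that FVC reflects fibrotic disease more directly than FEV1. Use of FEV1 and the CCQ in COPD patients, and the safety aim, are untouched. This should be corrected, at little cost.

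**What to change.** 1. Reconcile section 8 with section 9a and CL-005 part A, and state one study population.
2. If ILD is out, word the research questions, the hypotheses, the generalisation in section 6 and all efficacy conclusions for COPD only.
3. If ILD is in, amend sections 5a, 6, 10, 11c and 12b as follows:
   - Record FVC as well as FEV1 from the tests already scheduled before treatment and at 6 months.
   - Keep FEV1 as primary for COPD. Name change in FVC as the lung function outcome for ILD, with FEV1 also shown. Do not carry the 5 to 10% FEV1 target over to FVC.
   - Report COPD and ILD separately, with no pooled efficacy statement, and say in advance where a patient with both diagnoses is counted.
   - Confine the CCQ-based answer to question 3 to COPD, and label ILD patients' CCQ, journal and theme data exploratory.

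The cost is one more recorded value per test, some rewording, and fewer patients behind each statement. Question 3 would have only an exploratory answer for ILD, and the report should say so.

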## **3. AIM(S) OF STUDY**

Through the collection of qualitative and quantitative data, Lung Institute aims to explore and describe the safety and efficacy of autologous stem cell treatment for chronic lung disease with dissemination to the public and to the medical community for the advancement of regenerative medicine. The study aims to confirm the safety of autologous cell therapy, explore the effect of autologous cell therapy treatment on pulmonary function, and to describe the anecdotal quality of life changes of patients following treatment using both quantitative and qualitative measures.

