### **5c. Qualitative Arm**

An assumption of qualitative research is that no pre-determined hypothesis is made. Following autologous stem cell treatment for chronic lung disease, patients will report improvement in at least one of several quality of life indicators.

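### Section 12b reads the CCQ only for themes, so research question 3 on quality of life gets no amount of change and no interval

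*Combined protocol and SAP*

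**What the plan says.** Section 4 poses the third research question as one about change: "Does treatment with autologous stem cells for chronic lung disease improve the patient's perceived quality of life". Section 1 lists better results on quality of life scales among the hypothesised outcomes. Section 3 aims to describe "quality of life changes of patients following treatment using both quantitative and qualitative measures", and the word just before that quote qualifies the changes as anecdotal.

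Section 6 assigns quality of life to the qualitative arm, which collects "anecdotal data regarding perceived quality of life among treated patients" before and after treatment under an interpretive phenomenological approach.

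In section 12b, "Pre- and post-treatment FEV1 measurements will be collected on each patient and evaluated by simple measures of central tendency", namely mean, median and mode. For the qualitative arm, "Lung Institute utilizes CCQ, the Clinical COPD Questionnaire", and its analysis is stated in one sentence: "The information will be collected and interpreted by evaluating for common themes within the anecdotes". The rest of 12b discusses the rigour of qualitative work.

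Section 5c first states that "An assumption of qualitative research is that no pre-determined hypothesis is made" and then that "patients will report improvement in at least one of several quality of life indicators".

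On data collection, the Office Manager SOP (Step 3) obtains a quality of life survey at check-in on the first treatment day. Section 11 places quality of life follow-up at two weeks, three months and six months and makes the calls voluntary. Policy CL-005, section H, makes two call attempts for a quality of life survey at six months. Section 12a anticipates 200 patients.

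**The concern.** Whether quality of life improves is a question about direction and amount. A thematic reading can show what patients say has changed. It cannot give the average size of the change or the uncertainty around it. Section 12b plans no CCQ score, change from baseline, time point for analysis or summary statistic.

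One of the three research questions would therefore be answered by selected themes alone, although section 12b says the study will inform the public and the medical community about efficacy. The 5c expectation does not fill the gap. It contradicts the sentence before it, does not list the indicators, and sets no minimum change and no time point.

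**Working it through.** **1. Is a numerical analysis of quality of life planned anywhere?**

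| Place | What it provides for quality of life |
|---|---|
| Section 1 | An expectation of better scale results; no analysis |
| Section 3 | Quantitative and qualitative measures, in a sentence covering three aims |
| Section 5c | An expectation about indicators; no definition of improvement |
| Section 6 | Pre/post anecdotal data; the two arms combined, with no method given |
| Section 10 | Improvement in self-reported indicators as an anticipated outcome |
| Section 11 | Follow-up times and patient journals |
| Section 11c | A questionnaire described as attached |
| Section 12b | Themes only for the CCQ; numerical summaries for FEV1 only |
| CL-005 section H; Office Manager SOP Step 3 | Collection of surveys; no analysis |

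None of these assigns a score, a change from baseline or an interval to the CCQ. The attached questionnaire is not in the text available for review and may carry scoring instructions. That would not alter what 12b plans to analyse.

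**2. Can the planned sample size be reproduced?** No. Section 12a gives 200 without alpha, power, effect size, SD or dropout allowance, so there is no quality of life calculation to check.

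**3. What would a scored paired change add?** The inputs are n = 200 from section 12a, and n = 100 and n = 60 as assumed numbers of patients with both surveys. The documents give no expected response. The SD of the change is also not given, so results are in units of that SD.

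95% CI half-width for the mean change = t(0.975, n − 1) / √n

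- n = 200: 1.972 / 14.142 = 0.139 SD
- n = 100: 1.984 / 10 = 0.198 SD
- n = 60: 2.001 / 7.746 = 0.258 SD

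These values hold for any continuous paired change and are not specific to the CCQ. They show that useful precision is available even if half the patients lack a six-month survey. The themes-only plan yields no corresponding figure.

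**4. Can the effect of the 5c expectation be sized?** No. A calculation would need the number of indicators, the chance that each is reported better without real change, and their correlation. The documents give none of these and plan no count of improvers.

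**The case against.** The strongest defence is that this is a declared qualitative arm. Section 3 sets out to explore and describe, section 6 adopts a phenomenological pre/post approach, and thematic analysis is a legitimate way to study perceived quality of life. A mean with a confidence interval also goes beyond the FEV1 plan, which has no interval. All of this is fair, and it is why the thematic analysis should stay. It does not explain why a questionnaire is used, improvement on scales is expected, and no numerical summary of it is planned.

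A reader might infer more than the documents support in four ways:

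- **That section 3 promises a quantitative quality of life analysis which 12b then breaks.** This is one reading. The phrase closes a sentence covering safety, pulmonary function and quality of life. It may mean quantitative measures for the first two and qualitative for the third, which is how sections 6 and 12b divide the work.
- **That 5c is a per-patient responder rule which will inflate the share of improvers.** It may equally be a group-level expectation, and no count is planned.
- **That no before-after comparison is intended.** Section 6 does intend one, but as anecdotal data.
- **That a scored change would establish benefit.** All patients are treated and nobody is blinded (section 11b), so it would describe change only.

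The remedy has limits of its own. The SOP and CL-005 do not name their survey as the CCQ. Follow-up is voluntary. A survey completed at the clinic may differ from one obtained by telephone.

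**Conclusion.** The concern holds as a gap in the analysis plan. As written, section 12b gives research question 3 no amount of quality of life change and no interval. This rests on reading the text and needs no numerical assumption.

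The precision available from a scored change is a half-width of about 0.14 SD of the change at the planned 200 patients and about 0.20 SD at an assumed 100. It presumes that both surveys are the CCQ, that the CCQ yields a score, and that patients with both surveys resemble those without. The last presumption is doubtful when follow-up is voluntary.

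The 5c wording is a secondary fault. It is inconsistent with the sentence before it, and its harm arises only if results are reported against it. No size can be put on that harm. The gap is worth correcting and easily corrected; it does not invalidate the qualitative work.

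**What to change.** - **Section 12b:** add the within-patient change in CCQ score from first-day check-in to six months, the time point used for FEV1, once both surveys are confirmed to be the CCQ. Report the mean with its 95% confidence interval, described as uncontrolled, unblinded before-after change.
- **Voluntary follow-up:** report how many patients contribute, compare baseline scores of those with and without a six-month score, and note any difference in survey mode (clinic or telephone).
- **Thematic analysis:** keep it as a separate descriptive part.
- **Section 5c:** delete the expectation of improvement on some indicator.
- **ILD patients:** if they are included, as section 9a and CL-005 section A provide, show their scores separately, because the instrument is named for COPD. The conflict with section 8, which names COPD only, is a separate point to reconcile.

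The cost is wording in two sections and a little scoring work. If either survey is not the CCQ, the named measure or the form must change. Separate ILD scores will have wider intervals, and a scored result may look less favourable than selected themes.
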